| PT1   | x (xx.x%)             | x            | x (xx.x%)             | x            | x (xx.x%)             | x            |
| PT2   | x (xx.x%)             | x            | x (xx.x%)             | x            | x (xx.x%)             | x            |
| ....  | ....                  | ....         | ....                  | ....         | ....                  | ....         |
| PTx   | x (xx.x%)             | x            | x (xx.x%)             | x            | x (xx.x%)             | x            |

.....  
AE: Adverse Event

Note: Multiple records from the same subject are only counted once within the same category

**Table 14.3.1-14 Incidence of adverse events requiring significant additional therapy, regardless of study drug relationship, by primary system organ class, preferred term and treatment**

Safety Set

| System Organ Class (SOC)
Preferred Term (PT) | Intensive
(N=X)    |              | Relaxed
(N=X)      |              | Total
(N=X)        |              |
|---|-----------------------|--------------|-----------------------|--------------|-----------------------|--------------|
|   | Nr (%) of
Subjects | Nr of
AEs | Nr (%) of
Subjects | Nr of
AEs | Nr (%) of
Subjects | Nr of
AEs |
| All Body Systems                                | x (xx.x%)             | x            | x (xx.x%)             | x            | x (xx.x%)             | x            |
| SOC1  | x (xx.x%)             | x            | x (xx.x%)             | x            | x (xx.x%)             | x            |
| PT1   | x (xx.x%)             | x            | x (xx.x%)             | x            | x (xx.x%)             | x            |
| PT2   | x (xx.x%)             | x            | x (xx.x%)             | x            | x (xx.x%)             | x            |
| ....  | ....                  | ....         | ....                  | ....         | ....                  | ....         |
| PTx   | x (xx.x%)             | x            | x (xx.x%)             | x            | x (xx.x%)             | x            |
| SOC2  | x (xx.x%)             | x            | x (xx.x%)             | x            | x (xx.x%)             | x            |
| PT1   | x (xx.x%)             | x            | x (xx.x%)             | x            | x (xx.x%)             | x            |
| PT2   | x (xx.x%)             | x            | x (xx.x%)             | x            | x (xx.x%)             | x            |
| ....  | ....                  | ....         | ....                  | ....         | ....                  | ....         |
| PTx   | x (xx.x%)             | x            | x (xx.x%)             | x            | x (xx.x%)             | x            |

.....  
AE: Adverse Event

Note: Multiple records from the same subject are only counted once within the same category

**Table 14.3.1-15 Incidence of ocular adverse events requiring significant additional therapy, regardless of study drug relationship, by primary system organ class, preferred term and treatment**

Safety Set

| System Organ Class (SOC)
Preferred Term (PT) | Intensive
(N=X)    |              | Relaxed
(N=X)      |              | Total
(N=X)        |              |
|---|-----------------------|--------------|-----------------------|--------------|-----------------------|--------------|
|   | Nr (%) of
Subjects | Nr of
AEs | Nr (%) of
Subjects | Nr of
AEs | Nr (%) of
Subjects | Nr of
AEs |
| All Body Systems                                | x (xx.x%)             | x            | x (xx.x%)             | x            | x (xx.x%)             | x            |
| SOC1  | x (xx.x%)             | x            | x (xx.x%)             | x            | x (xx.x%)             | x            |
| PT1   | x (xx.x%)             | x            | x (xx.x%)             | x            | x (xx.x%)             | x            |
| PT2   | x (xx.x%)             | x            | x (xx.x%)             | x            | x (xx.x%)             | x            |
| ....  | ....                  | ....         | ....                  | ....         | ....                  | ....         |
| PTx   | x (xx.x%)             | x            | x (xx.x%)             | x            | x (xx.x%)             | x            |
| SOC2  | x (xx.x%)             | x            | x (xx.x%)             | x            | x (xx.x%)             | x            |
| PT1   | x (xx.x%)             | x            | x (xx.x%)             | x            | x (xx.x%)             | x            |
| PT2   | x (xx.x%)             | x            | x (xx.x%)             | x            | x (xx.x%)             | x            |
| ....  | ....                  | ....         | ....                  | ....         | ....                  | ....         |
| PTx   | x (xx.x%)             | x            | x (xx.x%)             | x            | x (xx.x%)             | x            |

.....  
AE: Adverse Event

Note: Multiple records from the same subject are only counted once within the same category

**Table 14.3.1-16 Deaths, by primary system organ class, preferred term and treatment**

**Safety Set**

| Principal Cause of Death
System Organ Class (SOC)
Preferred Term (PT) | Intensive
(N=X)    |              | Relaxed
(N=X)      |              | Total
(N=X)        |              |
|---|-----------------------|--------------|-----------------------|--------------|-----------------------|--------------|
|   | Nr (%) of
Subjects | Nr of
AEs | Nr (%) of
Subjects | Nr of
AEs | Nr (%) of
Subjects | Nr of
AEs |
| All Body Systems  | x (xx.x%)             | x            | x (xx.x%)             | x            | x (xx.x%)             | x            |
| SOC1  | x (xx.x%)             | x            | x (xx.x%)             | x            | x (xx.x%)             | x            |
| PT1   | x (xx.x%)             | x            | x (xx.x%)             | x            | x (xx.x%)             | x            |
| PT2   | x (xx.x%)             | x            | x (xx.x%)             | x            | x (xx.x%)             | x            |
| ....  | ....                  | ....         | ....                  | ....         | ....                  | ....         |
| PTx   | x (xx.x%)             | x            | x (xx.x%)             | x            | x (xx.x%)             | x            |
| SOC2  | x (xx.x%)             | x            | x (xx.x%)             | x            | x (xx.x%)             | x            |
| PT1   | x (xx.x%)             | x            | x (xx.x%)             | x            | x (xx.x%)             | x            |
| PT2   | x (xx.x%)             | x            | x (xx.x%)             | x            | x (xx.x%)             | x            |
| ....  | ....                  | ....         | ....                  | ....         | ....                  | ....         |
| PTx   | x (xx.x%)             | x            | x (xx.x%)             | x            | x (xx.x%)             | x            |

.....  
AE: Adverse Event

Note: Multiple records from the same subject are only counted once within the same category

**Table 14.3.1-17 Arterial Thomboembolic Events**

**Safety Set**

|  | Intensive
(N=X)    |              | Relaxed
(N=X)      |              | Total
(N=X)        |              |
|--|-----------------------|--------------|-----------------------|--------------|-----------------------|--------------|
|  | Nr (%) of
Subjects | Nr of
AEs | Nr (%) of
Subjects | Nr of
AEs | Nr (%) of
Subjects | Nr of
AEs |
| Arterial Thomboembolic Events (ATEs)*     | xx.x                  | x            | xx.x                  | x            | xx.x                  | x            |
| Nonfatal myocardial infarction            | xx.x                  | x            | xx.x                  | x            | xx.x                  | x            |
| Nonfatal stroke                           | xx.x                  | x            | xx.x                  | x            | xx.x                  | x            |
| Vascular death and death of unknown cause | xx.x                  | x            | xx.x                  | x            | xx.x                  | x            |

\* ATEs defined as nonfatal myocardial infarction, nonfatal stroke, vascular death and death of unknown cause

AE: Adverse Event

Note: Some patients may have experienced multiple events

**Section 14.3.2 – Listings of deaths, other serious and significant adverse events**

**Listings (Section 14.3.2)**

***Listing 14.3.2-1 Deaths, by treatment***

**Safety Set**

| Site / Subject Number | Age | Sex    | Race      | Date of Last Dose (YYYY-MM-DD) | Date of Death (YYYY-MM-DD) | Study Day* | Principal cause reported |
|-----------------------|-----|--------|-----------|--------------------------------|----------------------------|------------|--------------------------|
| XXX / XXX-XX          | XX  | Male   | Caucasian | YYYY-MM-DD                     | YYYY-MM-DD                 | XX         | ABCD                     |
| XXX / XXX-XX          | XX  | Female | Asian     | YYYY-MM-DD                     | YYYY-MM-DD                 | XX         | ABCD                     |
| XXX / XXX-XX          | XX  | XX     | XX        | YYYY-MM-DD                     | YYYY-MM-DD                 | XX         | ABCD                     |
| XXX / XXX-XX          | XX  | XX     | XX        | YYYY-MM-DD                     | YYYY-MM-DD                 | XX         | ABCD                     |
| XXX / XXX-XX          | XX  | XX     | XX        | YYYY-MM-DD                     | YYYY-MM-DD                 | XX         | ABCD                     |
| XXX / XXX-XX          | XX  | XX     | XX        | YYYY-MM-DD                     | YYYY-MM-DD                 | XX         | ABCD                     |
| XXX / XXX-XX          | XX  | XX     | XX        | YYYY-MM-DD                     | YYYY-MM-DD                 | XX         | ABCD                     |
| XXX / XXX-XX          | XX  | XX     | XX        | YYYY-MM-DD                     | YYYY-MM-DD                 | XX         | ABCD                     |
| .....                 |     |        |           |                                |                            |            |                          |

\*Relative to the first day of treatment (Baseline)

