**Listing 14.3.2-2 Serious adverse events, by treatment**

**Safety Set**

| Site / Subject Number | Age / Sex / Race | Adverse Event (REPORTED/ Preferred / System Organ Class) | Start Date (YYYY-MM-DD) / Study day | End Date (YYYY-MM-DD) / Study day | Duration (Days) | Severity | Relationship to Study Medication | Action Taken |
|-----------------------|------------------|--|-------------------------------------|-----------------------------------|-----------------|----------|----------------------------------|--------------|
| XXX / XXX-XX          | 55/M/Ca          | ABCD / abcd / abcd                                       | YYYY-MM-DD                          | YYYY-MM-DD                        | XX              | Mild     | Not susp                         | X            |
| XXX / XXX-XX          | 76/F/As          | ABCD / abcd / abcd                                       | YYYY-MM-DD                          | YYYY-MM-DD                        | XX              | Mod      | susp                             | X            |
| XXX / XXX-XX          | 55/M/Ca          | ABCD / abcd / abcd                                       | YYYY-MM-DD                          | YYYY-MM-DD                        | XX              | Sev      | Not susp                         | X            |
| XXX / XXX-XX          | 76/F/As          | ABCD / abcd / abcd                                       | YYYY-MM-DD                          | YYYY-MM-DD                        | XX              | Mild     | susp                             | X            |
| XXX / XXX-XX          | 55/M/Ca          | ABCD / abcd / abcd                                       | YYYY-MM-DD                          | YYYY-MM-DD                        | XX              | Mod      | Not susp                         | X            |
| XXX / XXX-XX          | 76/F/As          | ABCD / abcd / abcd                                       | YYYY-MM-DD                          | YYYY-MM-DD                        | XX              | Sev      | susp                             | X            |
| XXX / XXX-XX          | 55/M/Ca          | ABCD / abcd / abcd                                       | YYYY-MM-DD                          | YYYY-MM-DD                        | XX              | Mild     | Not susp                         | X            |

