**Listing 16.2.1-2 Screened subjects discontinued from study prior to randomization**

All subjects

---

| Site / Subject Number | Age / Sex / Race | Date of Discontinuation (YYYY-MM-DD) | Primary reason for discontinuation |
|-----------------------|------------------|--------------------------------------|------------------------------------|
| XXX / XXX-XX          | 55/M/Ca          | YYYY-MM-DD                           | Adverse Event                      |
| XXX / XXX-XX          | 76/F/As          | YYYY-MM-DD                           | Lost to follow-up                  |
| XXX / XXX-XX          | 55/M/Ca          | YYYY-MM-DD                           | Physician decision                 |
| XXX / XXX-XX          | 76/F/As          | YYYY-MM-DD                           | Pregnancy                          |
| XXX / XXX-XX          | 55/M/Ca          | YYYY-MM-DD                           | Screen failure                     |
| XXX / XXX-XX          | 76/F/As          | YYYY-MM-DD                           | Study terminated by sponsor        |
| XXX / XXX-XX          | 55/M/Ca          | YYYY-MM-DD                           | Technical problems                 |
| XXX / XXX-XX          | 76/F/As          | YYYY-MM-DD                           | Subject/guardian decision          |
| XXX / XXX-XX          | 55/M/Ca          | YYYY-MM-DD                           | Death                              |
| .....                 |                  |                                      |                                    |

---

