**Listing 16.2.7-4 Serious adverse events**

**Safety Set**

| Subject Number   | AE No | Adverse Event (REPORTED / Preferred / System Organ Class) | Start Date (YYYY-MM-DD) / Study Day | Stop Date (YYYY-MM-DD) / Study Day | Duration | Site       | Severity | Action Taken | Relation to Study Drug |
|------------------|-------|---|-------------------------------------|------------------------------------|----------|------------|----------|--------------|------------------------|
| Intensive |       |   |                                     |                                    |          |            |          |              |                        |
| XXX-XX           | X     | ABCD  | YYYY-MM-DD / X                      | YYYY-MM-DD / X                     | X        | Left       | Mild     | ABCD         | Susp                   |
| XXX-XX           | X     | ABCD  | YYYY-MM-DD / X                      | YYYY-MM-DD / X                     | X        | Right      | Mod      | ABCD         | Not susp               |
| XXX-XX           | X     | ABCD  | YYYY-MM-DD / X                      | YYYY-MM-DD / X                     | X        | Both       | Sev      | ABCD         | Susp                   |
| XXX-XX           | X     | ABCD  | YYYY-MM-DD / X                      | YYYY-MM-DD / X                     | X        | Non-Ocular | Mild     | ABCD         | Not susp               |
| Intensive |       |   |                                     |                                    |          |            |          |              |                        |
| XXX-XX           | X     | ABCD  | YYYY-MM-DD / X                      | YYYY-MM-DD / X                     | X        | Left       | Mild     | ABCD         | Susp                   |
| XXX-XX           | X     | ABCD  | YYYY-MM-DD / X                      | YYYY-MM-DD / X                     | X        | Right      | Mod      | ABCD         | Not susp               |
| XXX-XX           | X     | ABCD  | YYYY-MM-DD / X                      | YYYY-MM-DD / X                     | X        | Both       | Sev      | ABCD         | Susp                   |

NK: Not Known; AE No = Adverse Number

Severity: Mild=Mild, Mod=Moderate, Sev=Severe

Relationship to study drug: Not susp=Not suspected, Susp=Suspected

Action taken: 1=Study drug dosage adjusted/temporarily interrupted, 2=Study drug permanently discontinued due to this AE

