2.2 Analysis sets

The following are common analysis sets used across the project.

Randomized Set: The Randomised Population will consist of all randomised patients.

Full Analysis Set (FAS): The Full Analysis Set (FAS) comprises all subjects randomised and whom have at least one post-baseline efficacy value for BCVA.

Safety Set: The Safety Set will consist of all patients who received at least one application of study treatment and had at least one post-baseline safety assessment. The statement that a patient had no adverse events also constitutes a safety assessment.

Per-Protocol Set: The Per-Protocol Set (PPS) will consist of all patients in the FAS who followed the treatment regimen as randomised and completed the study without clinically significant protocol deviations. Clinically significant protocol deviations will be identified and documented prior to the database lock. Refer to “Protocol Deviations” study document for further details.¹

In order to derive the analysis set, protocol deviations (defined prior to DB lock; impact on analysis defined in this document) and non-protocol deviations (based on the definition of the analysis set/according to this document) need to be considered.

The protocol deviations are mainly used in excluding entire patients or particular data within a patient from the Per Protocol Set (PPS) and are described in the Protocol Deviation Plan. Furthermore - to derive the analysis sets, non-protocol deviations will be used. Table 2-1 Analysis set exclusion summary below gives a summary of the non-protocol deviations that exclude patients from each analysis set.

Table 2-1 Analysis set exclusion summary

Analysis Set (to be excluded from)	Non-Protocol Deviations
Full Analysis Set	Not in the Randomized set Did not have at least one post-baseline efficacy value for BCVA
Per Protocol Set	Not in FAS Clinically significant protocol deviation(s)
Safety Set	Did not receive at least one study treatment Did not record at least one post-baseline safety assessment

All efficacy evaluations will be carried out on the FAS. The analysis for the primary efficacy evaluation will be carried out on both the FAS and the PPS population. Analyses for secondary and exploratory evaluations will be carried out on the FAS, and may also be carried out on the PPS population as part of sensitivity analyses. Within the FAS and PPS, patients will be analysed as randomised.

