2.4.1.1 Baseline

Baseline is defined as the last available non-missing value collected just prior to the start of treatment in the study eye. Where a patient parameter value is missing for Visit 2:

1. If the patient has entered the treatment period (i.e. received at least one treatment), the baseline value for that patient will be imputed with the patient's Screening value.

2. If the patient never entered the treatment period, the baseline value will not be imputed.

Furthermore, patients with screening assessments, who do not enter the treatment period data, will only be included in data listings.

Note: Photography and FA performed no more than 14 days before the Baseline Visit will be accepted as the baseline examination (will not need to be repeated unless clinically indicated).

Note: BCVA performed no more than 2 days before the Baseline Visit will be accepted as the baseline examination. In addition, only BCVA data collected as per protocol (e.g. refracted ETDRS) will be accepted as the baseline examination.

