2.4.1.2 Post-baseline

All assessments obtained after the date of first dose of study drug are considered as post-baseline unless otherwise specified. Missing data for post-baseline values, for example due to discontinuation, loss to follow-up, or other types of censoring (e.g. due to rescue medication), will not be imputed. Only subjects with measurements at any given time point will be included in the analysis for that given parameter and visit. Refer to Section 2.4.3 for further details regarding the handling of missing dates.

The study day for a baseline or post-baseline scheduled or unscheduled visit is defined as:

$$\text{Study day} = (\text{Date of visit}) - (\text{date of first treatment}) + 1$$

The study day for a scheduled or unscheduled visit before baseline is defined as:

$$\text{Study day} = (\text{Date of visit}) - (\text{date of first treatment})$$

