2.9.1 Adverse events

Adverse events (AEs) will be reported by primary system organ class and preferred term according to the Medical Dictionary for Regulatory Activities (MedDRA).

The MedDRA version used for reporting the study will be described in a footnote.

AEs will be deemed treatment emergent if the onset date is on or after the date of first study treatment. Any AEs recorded prior to the start of study treatment will be listed together with all other AEs. If any event has an incomplete onset date, this will be handled as described in section 2.4.3.1 above.

The incidence of treatment emergent AEs will be summarized separately for ocular and non-ocular AEs as follows:

- All AEs
- AEs by maximum severity
- AEs suspected to be related to study drug
- Serious AEs
- AEs leading to study treatment discontinuation

Patients who experienced multiple adverse events for a preferred term will be counted once, similarly for patients with multiple adverse events per system organ class.

All information pertaining to AEs noted during the study will be listed by patient, detailing AE (e.g., verbatim given by the investigator as well as the system organ class and preferred term according to MedDRA), date of starting and ending, severity, suspected relationship (by the investigator) to the study drug / ocular injection, and eye (for ocular events). The AE onset will also be shown relative (in number of days) to the day of (first) initial study treatment (ranibizumab injection) and relative (in number of days) to the Day 1.

The following AE listings will be provided:

- All adverse events,
- Ocular adverse events
- Adverse events suspected to be related to study drug and/or ocular injection.
- Serious adverse events,
- Adverse events leading to treatment withdrawal
- Adverse events leading to treatment interruption

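### The death, SAE and AE listings are limited to the Safety Set, so event detail is lost for never-treated patients, and a treated patient with only injection-day safety data drops out of the AE tables

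*Protocol*

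**What the plan says.** The document supplied as the Protocol is a set of output shells. Section 14.3.2 contains "Listing 14.3.2-1 Deaths, by treatment" and "Listing 14.3.2-2 Serious adverse events, by treatment", and Section 16.2.7 contains "Listing 16.2.7-4 Serious adverse events" and the all-AE listing 16.2.7-1. All four are headed Safety Set, as is the deaths table 14.3.1-16.

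SAP 2.2 admits to the Safety Set patients who "received at least one application of study treatment and had at least one post-baseline safety assessment". SAP Table 2-1 and the footnote to shell Table 14.1-7 repeat this. A recorded statement that the patient had no AEs counts as an assessment. SAP 2.4.1.2 then fixes the timing: "All assessments obtained after the date of first dose of study drug are considered as post-baseline unless otherwise specified".

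On listings, SAP 2.9.1 undertakes to list by patient everything recorded about AEs during the study, and adds: "Any AEs recorded prior to the start of study treatment will be listed together with all other AEs". SAP 2.4.1.1 says that "patients with screening assessments, who do not enter the treatment period data, will only be included in data listings". On the other side, SAP 2.2 and 2.9 place safety evaluations and analyses on the Safety Set, and the AE listings named in 2.9.1 do not include one for deaths.

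**The concern.** A listing of deaths and SAEs is where a reader looks for every such event, with enough detail to judge it. Two groups are at risk if these listings are programmed as headed.

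The first is patients who consented but were never treated, whether or not they were randomised. The shells provide for such events. Listing 16.2.1-2, "Screened subjects discontinued from study prior to randomization", shows death and adverse event among its example reasons for leaving. Tables 10-1 and 14.1-1 carry the same reasons on the Randomised Set, with a separate row for patients who started treatment. The number of deaths in the disposition table therefore need not agree with the number in the death listing or in Table 14.3.1-16, and no listing would explain a difference.

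The second is a treated patient with an event on the day of the first injection and nothing recorded afterwards. Injection-day events are of direct interest for an intravitreal drug.

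**Working it through.** There is no planned figure to reproduce. The check is to follow each type of patient through the population headings.

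| Patient | In Safety Set? | What the shells show | What is missing |
|---|---|---|---|
| Screened, not randomised | No (untreated) | Count by reason in Table 14.1-2; date and reason in Listing 16.2.1-2 | Cause of death; SAE term, severity, causality; any SAE that did not end participation |
| Randomised, never treated | No (untreated) | Count by reason in Tables 10-1 and 14.1-1; date and reason in Listing 16.2.4-1 | Same |
| Treated, only safety record dated the first-injection day | No, read literally | Disposition outputs only | All AE tables and listings |
| Treated and assessed later, SAE before first injection | Yes | Listed: the AE and SAE listings have no onset restriction | Nothing |

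**Never-treated patients.** The detail lost is what the headed listings would have carried. Listing 14.3.2-1 has a column for principal cause of death. Listing 14.3.2-2 has reported and preferred terms, start and end dates, severity, relationship and action taken. The disposition listings have none of these columns beyond a date and a reason. I looked for another output that could fill the gap. Listing 16.2.1-1 is on the Full Analysis Set. The in-text section on deaths and SAEs in Section 12 says there is none. Section 14.3.3 assigns narratives to non-biometric deliverables and states no population.

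**Injection-day data.**
1. SAP 2.2 requires at least one post-baseline safety assessment.
2. SAP 2.4.1.2 makes an assessment post-baseline only if it comes *after* the date of first dose. The rule allows exceptions, but neither SAP 2.2 nor 2.9 makes one for safety assessments.
3. SAP 2.9.1 makes an AE treatment-emergent if its onset is *on or after* that date.
4. So an AE with onset on the first-dose date is treatment-emergent, but a safety record of the same date does not admit the patient to the Safety Set. If that is the only record, the patient and the event leave all the AE tables.

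**Effect of one such patient.** Take the planned 165 patients per arm (SAP 2.12) and an event seen in that patient alone. The arm incidence is 1/165 = 0.61% with the patient and 0/164 = 0% without, a change of about 0.6 percentage points.

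**The case against.** The strongest defence is that the shells follow the SAP, since SAP 2.2 and 2.9 put safety on the Safety Set. The sentence on pre-treatment AEs sorts events by time and names no population, so a treated patient's pre-injection AE would satisfy it. The sentence in SAP 2.4.1.1 sits in the section on baseline and does not say which listings it means; Listing 16.2.1-2 is one. This stands far enough that a reader should not infer that the SAP says the opposite of the shells. For deaths, any promise to list is inferred. It does not dispose of the general undertaking in SAP 2.9.1 to list all AE information by patient, which the headings do not deliver for untreated patients.

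Two further readings are tempting and wrong. One is that these deaths and SAEs are described nowhere. A death, or an AE that ended participation, does appear with date and reason in the disposition outputs, and narratives outside these documents may cover more. The other is that all events between consent and first injection are lost. The Safety Set filters patients, not dates, so an SAE before injection in a patient who later enters the set is still listed.

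The injection-day group is also narrow. A bare statement of no AEs after that day is enough to qualify, and SAP section 1 asks withdrawn patients back about 30 days after their last visit. That makes the case rare but does not reconcile the two definitions.

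**Conclusion.** The point holds within limits. As headed, the four listings omit the cause of death and the SAE term, severity and causality for never-treated patients, and an SAE that did not end such a patient's participation appears in no output. Separately, the mismatch between *after* and *on or after* can remove a treated patient, and that patient's event, from every AE table.

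The number affected is probably very small and cannot be estimated. The documents do not give the number screened and untreated, the number randomised and untreated, the number treated without later assessment, or an SAE rate. Screening lasts at most two weeks and randomisation follows confirmation of eligibility at the Baseline Visit (SAP section 1), so randomised but untreated patients should be few. Whether AEs are collected from screening failures depends on the clinical study protocol cited in the SAP, which is not among these documents. The conclusion rests on the outputs being programmed as headed and the Safety Set being applied as written. It is a cheap improvement to completeness and reconciliation and does not touch the efficacy conclusions.

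**What to change.** 1. Head Listings 14.3.2-1, 14.3.2-2, 16.2.7-1 and 16.2.7-4 *All subjects*, meaning all consented patients including those not randomised. Avoid *All Enrolled*: in these shells it heads outputs by arm (Tables 14.1-7 and 14.1-8, Listing 16.1.7-1) and could still omit patients who were not randomised.
2. Add a status column (not randomised / randomised, not treated / treated). Listings sort by treatment group (shell section 1.2.3), so add a *not randomised* group to the sort order. Leave study day blank where there was no treatment.
3. Define the Safety Set as all patients who received at least one study treatment, by deleting the post-baseline assessment clause in SAP 2.2, SAP Table 2-1 and the Table 14.1-7 footnote. This also removes the first-dose-day mismatch.
4. Keep the incidence tables on treated patients.

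The cost is minor programming. Denominators may rise by a few treated patients without follow-up, which would lower incidences slightly where those patients had no event.
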